Local Anesthesia for Ultrasound
Guided Hip Joint Injections: A
Double-Blind Randomized
Controlled Trial of
Bacteriostatic Saline versus
Buffered Lidocaine

NCT# 02209272

July 1, 2014

Title: Local Anesthesia for Ultrasound Guided Hip Joint Injections: A Double-Blind Randomized Controlled Trial of Bacteriostatic Saline versus Buffered Lidocaine

Principal investigator: [name]

Co-investigators: [name]
[name]
[name]

Statistician: [name], M.S.

Abstract:

Local anesthesia is commonly used to reduce pain during joint injections, particularly for deep joints like the hip. Lidocaine is the most commonly used local anesthetic in most medical practices. It is well known that lidocaine infiltration itself is painful. Many strategies have been studied to minimize pain associated with lidocaine administration, including buffering, warming, and slowing infiltration rate. Bacteriostatic saline (BS) is an alternative local anesthetic that has been shown to be less painful when injected into subcutaneous tissues compared with lidocaine. However, BS use has not been widely implemented for local anesthesia, and it has not been studied in the context of joint injections. The purpose of this study is to compare infiltration pain and anesthetic efficacy between lidocaine and BS for ultrasound (US) guided intraarticular hip injections.

Primary Aims:

1. To compare subcutaneous/intramuscular infiltration pain of BS versus buffered 1% lidocaine *prior to* US guided intraarticular hip injections.
2. To compare local anesthesia efficacy of BS versus buffered 1% lidocaine *during* US guided intraarticular hip injections.

Hypotheses:

1. BS infiltration into subcutaneous and intramuscular tissue is significantly less painful than buffered 1% lidocaine.
2. US guided intraarticular hip injections are equally or less painful after local anesthesia with BS versus buffered 1% lidocaine infiltration.

Background and Significance:

Local anesthesia has been shown to significantly reduce pain associated with needle procedures (6). The most commonly used local anesthetic is lidocaine. It is well known that lidocaine infiltration into tissues is painful. Numerous strategies have been studied and utilized to attempt to minimize the pain of lidocaine infiltration.

Much of the pain associated with lidocaine infiltration is thought to be due to its acidic pH. Physiologic pH is between 7.35 and 7.45, whereas lidocaine formulations currently available on the market range from pH 3.5 to 7.0. Therefore, buffering lidocaine with sodium bicarbonate increases the pH to values more similar to physiologic pH, resulting in reduction of pain upon infiltration (3,4,7). Additionally, slowing the administration rate has been shown to reduce infiltrative discomfort (7). Warming local anesthetics to body temperature is another simple and inexpensive way to reduce discomfort of administration (5), though this is not a widespread practice.

Ultrasound (US) guidance for peripheral musculoskeletal procedures has become increasingly popular over recent years. US allows clinicians to avoid important neurovascular structures when advancing a needle toward a given target, which may improve procedure safety. Furthermore, US guidance improves accuracy of needle placement and medication deposition as the needle tip and target may be easily visualized to ensure proper needle positioning prior to agent administration. However, procedure length inevitably increases when the proceduralist takes time to make fine adjustments in needle placement prior to injecting. The potential for patient discomfort likely increases with the length of time the needle is within tissues. Therefore, local anesthesia is commonly used during US guided procedures, particularly deep injections such as the hip joint, to minimize discomfort and improve patient experience.

All US-guided hip injections will be completed using a cart-based Philips ultrasound machine in either the Sports Medicine Center, Mayo-14 PM&R Clinic, or Gonda Musculoskeletal Clinic. US-guided local anesthetic administration will be completed using a 25-gauge, 2-inch stainless steel needle. US-guided hip injections will be completed using a 22-gauge, 3.5-inch stainless steel needle. The equipment for this study is available in each respective clinic and will be used at no additional cost.

Study Subjects

Mayo Clinic patients 18-75 years old referred for US-guided intraarticular hip injections in the Sports Medicine Center, Mayo-14 PM&R Clinic, or Gonda-14 Musculoskeletal Clinic.

Exclusion criteria will include: (1) chronic opioid use, (2) opioid use on day of procedure, (3) history of fibromyalgia or other diffuse chronic pain syndrome, (4) pain behavior during the clinical encounter as judged by the injectionist, or (5) anesthetic administration time outside the designated 5-15 second time frame.

Sample Size

The primary outcome will be the VAS for Pain score during local anesthesia infiltration. We will use two-sample t-tests to compare the mean VAS for Pain scores between the two groups at each of the three time points. Based on prior studies assessing the VAS for Pain, 14 can be considered the minimal clinically important difference when assessing moderate pain levels (10-12). At test significance level (α) = 0.05 with 80% power, a difference in means ($\mu_1 - \mu_2$) = 14 with common standard deviation (σ) = 20, i.e. an effect size ($\delta = |\mu_1 - \mu_2|/\sigma$) = 0.70, can be detected when the sample size (n) per group is 34 (68 total subjects). Since data will be collected at a single point of care, we anticipate a low dropout rate of approximately 10%. Therefore, total sample size for the study will be 76 patients after adjusting for dropouts.

Data Collection

Data collection is described above in *Study Design*. The non-injecting author ([name]) will collect and collate the data.

Data Handling/Processing

The data will be compiled on an Excel® file for data analysis. The computer files will be stored in the primary investigator's H-drive of Mayo Clinic's computer network.

Data Analysis

Patient demographic characteristics data will be summarized and compared between the two treatment arms. Mean \pm SD for continuous variables and frequency (% percentage) for categorical variables will be given. Differences between arms will be tested using Wilcoxon tests for continuous variables and chi-square tests for categorical variables. Differences in adverse events between arms will be tested using chi-square tests. The mean VAS for Pain score prior to and during local anesthesia infiltration will be compared between the 2 groups by two-sample t-tests or Wilcoxon Rank sum tests when appropriate. Changes in pain from baseline will also be compared between arms using t-tests or Wilcoxon tests as appropriate. A generalized linear model (GLM) will be used to compare the two groups after adjusting for age, gender and baseline VAS pain score. Mixed effects models will be fit to model the longitudinal VAS pain scores. The primary analysis will be based on patients with anesthetic administered within the targeted 5-15 second infiltration window. However, an intent-to-treat analysis will also be performed, including patients that had anesthetic administered outside of the 5-15 second window. For all analyses, two-sided tests will be used and p-values less than 0.05 will be considered as statistically significant. All statistical analyses will be performed by SAS 9.3 version software (SAS institute Inc., Cary NC).

Adverse Event Stopping Rule

The stopping rule specified below is based on the knowledge available at study development. We note that the Adverse Event Stopping Rule may be adjusted in the event of either (1) the study re-opening to accrual or (2) at any time during the conduct of the trial and in consideration of newly acquired information regarding the adverse event profile of the treatments under investigation. The study team may choose to suspend accrual because of unexpected adverse event profiles that have not crossed the specified rule below. CTCAE v4.0, a grading system for adverse event severity, will be used to determine grading for these stopping rules.

Study accrual will be temporarily suspended if at any time we observe events considered at least possibly related to study treatment (i.e., an adverse event with attribute specified as “possible”, “probable”, or “definite”) that satisfy the following:

- if 5 or more patients in the first 20 treated patients (or 25% of all patients after 20 are accrued) experience a grade 2 (moderate) or higher adverse event, and the adverse event incidence rate is higher in the BS arm than the lidocaine arm.

We note that we will review grade 4 (life-threatening) and 5 (death) adverse events deemed “unrelated” or “unlikely to be related”, to verify their attribution and to monitor the emergence of a previously unrecognized treatment-related adverse event.

After the first 20 patients are treated, accrual will also be temporarily suspended if there is significantly more pain after baseline on the BS arm.

Feasibility and Time Frame

Over 5,000 US guided injections are performed yearly in these three clinics combined, and a significant portion are intraarticular hip injections. We estimate it will take 6-12 months to recruit the patients. Patients will not need to be referred specifically for the study, as they will be recruited at the time of presentation for routine US guided hip injection. The study will likely add about 5-10 minutes to the typical US guided hip injection visit.

Strengths

There are several reasons this study has the potential to change the widespread practice of lidocaine local anesthesia prior to US guided hip joint injections. BS is a safe alternative local anesthetic with several potential advantages over lidocaine, including lower cost, less painful infiltration, and similar efficacy. Patients would be subjected to no additional risk or cost over routine US guided injections. Lower cost of BS would decrease health care costs. Less painful anesthetic infiltration and similar efficacy would minimize patient discomfort and improve patient experience.

Limitations

A limitation of this study design is that it will be specific to the hip joint, which is likely the US guided injection for which local anesthesia is most commonly used. Although similar efficacy would be expected in other body regions, the comparison of BS versus lidocaine may not be valid for other musculoskeletal injections.

Human Subjects:

Detailed Description and Population

For subject details and inclusion/exclusion criteria, see *Study Subjects* section above.

Research Materials

As noted above, pain will be assessed using a VAS for Pain scale.

Recruitment of Subjects

All recruitment will occur directly with patients via a telephone call prior to their scheduled hip injection or at the point of care. An email will be sent to our PM&R and Sports Medicine colleagues to increase awareness and encourage internal referral for US guided intraarticular hip injections.

Potential Risks

The control group will receive the same treatment as is currently being provided with US guided hip joint injections. The BS group will be subjected to no increased risks relative to routine US guided hip joint injection. BS manufacturer indications include

subcutaneous and intramuscular injection. Animal studies have shown that 0.75% BS intramuscular and perineural injections cause no histological tissue damage (14,15). Furthermore, the BS manufacturer literature states “adverse reactions to intravenous, intramuscular, or subcutaneous injection of 0.9% benzyl alcohol are not known to occur in man... preparations containing 0.9% benzyl alcohol in several species of animals have indicated that an estimated intravenous dose of up to 30 mL may be safely given to an adult without toxic effects.” In this study, only 3 mL will be administered (subcutaneous/intramuscular) in each BS group subject.

Protection

Subjects will be provided with a contact number to call if any concerns arise. In the event of an adverse reaction or complication, the patient will be handled no differently than he/she would be following routine injections. Full evaluation and management will be provided as indicated.

As noted above in *Study Design*, subjects will be contacted 2 weeks post-procedure to assess for adverse events. After the first 20 patients have been completed, the non-injecting author ([name]) will assess the data for concerning trends in pain scores and adverse events in the BS group. If there are significantly elevated pain scores or more adverse events in the BS group, the study will be stopped.

Benefits

As noted above, preliminary studies have shown BS to be a safe alternative local anesthetic with potential advantages over lidocaine, including less painful infiltration and similar efficacy. BS has potential to minimize patient discomfort and improve patient experience associated with US guided injections without increasing procedural risks or cost.

Gender/Minority Mix:

This study will be available to all eligible patients, regardless of race or ethnic origin. There is no information currently available regarding differential effects of BS in subsets defined by race or ethnicity, and there is no reason to expect such differences to exist. Nonetheless, the planned analyses will, as always, look for differences in treatment effect based on racial groupings.

Based on current treatment practice, we expect about 10% of patients will be classified as minorities by race and 50% of patients will be women in the study accrual. Expected sizes of racial subsets are shown in the following table:

Accrual Targets			
Ethnic Category	Sex/Gender		
	Females	Males	Total
Hispanic or Latino	1	1	2

Not Hispanic or Latino	37	37	74
Ethnic Category: Total of all subjects	38	38	76
Racial Category			
American Indian or Alaskan Native	0	0	0
Asian	1	1	2
Black or African American	3	3	6
Native Hawaiian or other Pacific Islander	0	0	0
White	34	34	68
Racial Category: Total of all subjects	38	38	76

Ethnic Categories:

Hispanic or Latino – a person of Cuban, Mexican, Puerto Rican, South or Central American, or other Spanish culture or origin, regardless of race. The term “Spanish origin” can also be used in addition to “Hispanic or Latino.”

Not Hispanic or Latino

American Indian or Alaskan Native – a person having origins in any of the original peoples of North, Central, or South America, and who maintains tribal affiliations or community attachment.

Asian – a person having origins in any of the original peoples of the Far East, Southeast Asia, or the Indian subcontinent including, for example, Cambodia, China, India, Japan, Korea, Malaysia, Pakistan, the Philippine Islands, Thailand, and Vietnam. (Note: Individuals from the Philippine Islands have been recorded as Pacific Islanders in previous data collection strategies.)

Black or African American – a person having origins in any of the black racial groups of Africa. Terms such as “Haitian” or “Negro” can be used in addition to “Black or African American.”

Native Hawaiian or other Pacific Islander – a person having origins in any of the original peoples of Hawaii, Guam, Samoa, or other Pacific Islands.

White – a person having origins in any of the original peoples of Europe, the Middle East, or North Africa.

Racial Categories:

References:

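### The primary comparison is tied to an unadjusted t-test; leading with the covariate-adjusted model already planned would be a cheap improvement with a small downside, not the repair of an error

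*Combined protocol and SAP*

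**What the plan says.** Sample Size defines the endpoint: "The primary outcome will be the VAS for Pain score during local anesthesia infiltration". The next sentence gives the method: "We will use two-sample t-tests to compare the mean VAS for Pain scores between the two groups at each of the three time points". The calculation that follows is for that test, with no allowance for covariates.

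Data Analysis lists several methods: a t-test or Wilcoxon rank sum test on the scores, the same tests on change from baseline, an adjusted model, and mixed models for the longitudinal scores. The adjusted model reads: "A generalized linear model (GLM) will be used to compare the two groups after adjusting for age, gender and baseline VAS pain score". All of them share one threshold: "For all analyses, two-sided tests will be used and p-values less than 0.05 will be considered as statistically significant".

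Data Analysis does not say which method supplies the primary result. Where it speaks of the primary analysis, it defines only the population, namely patients whose infiltration took 5 to 15 seconds.

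Study Design states that the baseline VAS rates hip pain before the procedure and that the second VAS rates infiltration pain. It describes computer randomization and mentions no stratification.

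**The concern.** The one method tied to the primary outcome ignores three pre-treatment variables that the investigators themselves chose as covariates. If those variables predict infiltration VAS, the t-test leaves predictable between-patient variation in its error term, and chance differences between arms in those variables add noise to the estimate. Nothing described in the design balances them. The adjusted model would remove that noise, and it needs no data that the trial does not already collect.

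There is a related matter of ranking. Several methods are planned at the same threshold, and they can disagree. Naming one in advance prevents the headline from being chosen after the results are seen.

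At stake are a few points of power and the clarity of the primary result. The validity of the trial is not in question.

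**Working it through.** **Inputs from Sample Size and Data Analysis**
- Difference 14 mm: "14 can be considered the minimal clinically important difference when assessing moderate pain levels".
- SD 20 mm: "14 with common standard deviation".
- Two-sided alpha 0.05 and 80% power: "0.05 with 80% power, a difference in means".
- 34 per group: "can be detected when the sample size (n) per group is 34 (68 total subjects".
- Covariates: age, gender and baseline VAS, so q = 3.

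**Assumed input.** R is the joint (multiple) correlation of the three covariates with infiltration VAS. The documents give no value, so a range of 0 to 0.5 is shown.

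**Step 1. Reproduce the plan's figure.**
- Standard error of the difference = 20 × √(2/34) = 4.85 mm.
- Noncentrality = 14 / 4.85 = 2.886, on 66 df.
- Exact noncentral t power: 81.2% at 34 per group and 79.97% at 33. The smallest n that reaches 80% is therefore 34, as stated.
- Dropout: 68 / 0.9 = 75.6, rounded up to 76, as stated.

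**Step 2. Power of the adjusted model at the same n.** Three things change:
- The residual SD falls to 20 × √(1 − R²).
- The residual df fall to 68 − 2 − 3 = 63.
- The variance of the treatment estimate is inflated on average by 1 + q/(N − q − 3) = 1 + 3/62 = 1.048, because the covariates differ by chance between arms.

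Noncentrality = 14 / [20 × √(1 − R²) × √(2/34 × 1.048)].

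| R | R² | Residual SD (mm) | Noncentrality | Power | Against 81.2% |
|---|---|---|---|---|---|
| 0 | 0 | 20.0 | 2.819 | 79.3% | −1.9 |
| 0.2 | 0.04 | 19.6 | 2.877 | 80.9% | −0.3 |
| 0.3 | 0.09 | 19.1 | 2.955 | 82.9% | +1.7 |
| 0.4 | 0.16 | 18.3 | 3.076 | 85.7% | +4.5 |
| 0.5 | 0.25 | 17.3 | 3.255 | 89.3% | +8.1 |

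The inflation factor matters. Removing only the 3 df would give 81.1% at R = 0 and make adjustment look almost free. With the factor included, the loss is about 2 points.

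**Step 3. Thresholds.**
- The adjusted model matches the t-test at R² of about 0.048, that is R of about 0.22.
- It reaches the planned 80% at 34 per group once R is about 0.14. At R = 0 it would need 35 per group.

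**Step 4. Check by simulation.** With 20,000 trials per scenario, the adjusted model's power was 79.2%, 80.9%, 82.9%, 86.2% and 89.2% at R = 0, 0.2, 0.3, 0.4 and 0.5. The t-test stayed between 81.0% and 81.6%.

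**Step 5. Why the ranking matters.** Suppose baseline and infiltration VAS both have SD 20 and correlate 0.3 (assumed). The change score then has SD 20 × √(2 × 0.7) = 23.7 mm. The planned change-from-baseline t-test has 67.1% power for 14 mm, against 82.9% for the adjusted model at R = 0.3. The listed methods are not interchangeable.

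**The case against.** The strongest case against acting is that nothing here is wrong. An unadjusted t-test in a randomized trial is valid. Chance imbalance is already reflected in its standard error, so it is not bias. The sample size reproduces, sizing on the simpler test is ordinary practice, and the adjusted estimate will be produced anyway. All of this stands, and it is why the point is an improvement and not an error.

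The benefit also rests on an unknown. Baseline VAS rates hip pain, a different stimulus from infiltration, and Progress Report and Preliminary Studies reports no earlier work with bacteriostatic saline in joint or soft tissue injections. A value of R below 0.22 cannot be ruled out. This stands too. Against it, the same patient marks the same 100 mm line at each rating within one visit, and age and gender may add something. A joint R above 0.22 is therefore plausible, although the documents do not establish it.

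Three stronger readings are tempting:
- A reader might infer that adjustment gains power at no cost. It does not: if the covariates predict nothing, it costs about 2 points.
- A reader might infer that 34 per group becomes conservative under the adjusted model. That is so only above break-even. Below R of about 0.14, power is slightly under 80%.
- A reader might infer that the plan fixes the unadjusted result as the headline. Sample Size points that way, but Data Analysis names no primary method.

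**Conclusion.** This is an optional but worthwhile change to the analysis wording. The t-test is valid, and 34 per group (76 in total) is correct for it on the plan's own inputs. Over R from 0 to 0.5, leading with the adjusted model changes power by about −2 to +8 points, with break-even near R = 0.22 and gains of about 4.5 to 8 points at R of 0.4 to 0.5.

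These figures rest on the plan's 14 mm and SD 20, 34 analysed patients per group, a normal linear model with three covariates, and an R that the documents do not give. The small worst-case loss, set against a larger possible gain and a clearly named primary analysis, favours the change. The documents do not support calling the t-test biased or the trial underpowered on this ground.

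**What to change.** Before unblinding, state in Data Analysis that the primary analysis of infiltration VAS is a normal linear model with terms for arm, age, gender and baseline VAS, and that it supplies the treatment difference, 95% CI and p-value. Keep the t-test or Wilcoxon rank sum test as supportive, and align the sentence in Sample Size with this.

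Keep 76 patients. Add a sentence saying that the sample size was calculated for the unadjusted t-test, and that the adjusted model's power depends on an unknown R (79.3% to 89.3% for R from 0 to 0.5).

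The cost is a few sentences, with no additional patients, data or visits. The statistical risk is the loss of up to about 2 points of power if the covariates predict little.

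### Chi-square is the only test named for adverse events and categorical variables, with no alternative for small counts (minor)

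*Combined protocol and SAP*

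**What the plan says.** Data Analysis covers counts in two sentences. For patient characteristics: "Differences between arms will be tested using Wilcoxon tests for continuous variables and chi-square tests for categorical variables". For safety: "Differences in adverse events between arms will be tested using chi-square tests". Neither mentions an exact test, a continuity correction or a rule for small counts. For pain scores, the same paragraph does allow a choice, "two-sample t-tests or Wilcoxon Rank sum tests when appropriate". It then applies one criterion throughout: "For all analyses, two-sided tests will be used and p-values less than 0.05 will be considered as statistically significant".

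The documents give no expected adverse event rate. Potential Risks quotes the manufacturer to the effect that "adverse reactions to intravenous, intramuscular, or subcutaneous injection of 0.9% benzyl alcohol are not known to occur in man", and says the saline arm carries no added risk over routine injection. Gender/Minority Mix says "we expect about 10% of patients will be classified as minorities by race", and its accrual table targets 2 Hispanic, 2 Asian and 6 Black patients out of 76.

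**The concern.** The chi-square p-value is a large-sample approximation, and the usual caution applies when expected counts fall below 5. The plan provides for doubtful assumptions when it analyses pain but not when it analyses counts. If adverse events turn out to be few, the plan as written requires the approximation and labels the result significant or not on that basis. A split of a few events could then be reported as a safety difference between the agents although exact tests do not support it. If the choice of test were made after the data were seen, it would be a choice between tests that disagree. A bare p-value also does not show how much harm a low or zero count leaves possible.

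**Working it through.** **Inputs.** Sample Size gives 34 per group (68) and 76 after dropout. Equal arms are inferred from the per-group wording, hence 38 per arm. Alpha is 0.05, two-sided (Data Analysis). The adverse event rate is not stated, so a range is assumed below.

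**The plan's own figure.** For a difference of 14, SD 20 and 80% power, the normal formula gives 33 per arm. The exact t-test calculation gives 33.02, rounded up to 34 (power 81.2%). Then 68/0.90 = 75.6, or 76. The stated sample size is reproduced. It concerns pain; no power or rate is stated for the adverse event test.

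**When counts are small.** With equal arms, the expected number of events per arm is m/2 for m patients with an event. It is below 5 when m ≤ 9, and 9/76 = 11.8%. The chance of m ≤ 9 under assumed true rates (both arms alike, binomial with 76 patients) is:

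- 5%: 0.995
- 10%: 0.77
- 15%: 0.28
- 25%: 0.004

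The accrual targets give expected counts per arm of 1 (Hispanic), 1 (Asian) and 3 (Black). So 2 of 4 ethnicity cells, and 4 of 6 race cells once empty categories are dropped, are below 5.

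**Where the tests differ, 38 per arm.** For a v b events with m = a + b, the uncorrected statistic is 76(a − b)²/[m(76 − m)]. For 4 v 0 it is 76 × 16/(4 × 72) = 4.22, p = 0.040. For 6 v 1 it is 76 × 25/(7 × 69) = 3.93, p = 0.047. Fisher for 4 v 0 is 2 × C(38,4)/C(76,4) = 2 × 73,815/1,282,975 = 0.115.

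| Split | Chi-square | Fisher | Boschloo | Barnard |
|---|---|---|---|---|
| 4 v 0 | 0.040 | 0.115 | 0.085 | 0.0505 |
| 5 v 0 | 0.021 | 0.054 | 0.033 | 0.022 |
| 6 v 1 | 0.047 | 0.108 | 0.079 | 0.058 |
| 7 v 1 | 0.025 | 0.056 | 0.033 | 0.029 |

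All three exact tests contradict chi-square at 4 v 0 and 6 v 1. At 5 v 0 and 7 v 1 only Fisher does.

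**False-positive rate in equally safe arms.** Given the event total (hypergeometric), the chance of chi-square p < 0.05 is:

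- 1 to 3 events: 0%
- 4 events: 11.5%
- 5 events: 5.4%
- 6 events: 2.5%
- 7 events: 10.8%
- 8 events: 5.6%
- 9 events: 2.8%
- 10 events: 8.6%

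Averaged over all totals (two independent binomials of 38):

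| True rate | Chi-square | Fisher |
|---|---|---|
| 1% | 0.08% | below 0.01% |
| 2% | 0.6% | 0.01% |
| 3% | 1.7% | 0.06% |
| 5% | 4.1% | 0.3% |
| 10% | 5.8% (about the maximum) | 1.5% |
| 25% | 5.1% | 2.8% |

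**What a zero count leaves open.** For 0 of 38, the upper limit of the exact 95% interval is 1 − 0.025^(1/38) = 9.3%.

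**The case against.** The strongest reply is that the named test performs acceptably overall. If events are as rare as the protocol suggests, chi-square rejects less often than 5%. At worst it exceeds 5% by less than one percentage point. The high conditional figures at 4, 7 and 10 events are peaks of a sawtooth, and the totals between them give 5.6% or less. This stands, and it limits the point to particular tables.

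Much of the gap from Fisher is Fisher's own conservatism, and small expected counts do not fully explain it. The two tests also part at 8 v 2 (0.042 and 0.086), where the expected count is exactly 5. Barnard at 4 v 0 is barely above 0.05 with 38 per arm, and with 34 per arm it is 0.041. This stands too, although Boschloo at 34 per arm (0.068) still exceeds 0.05.

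Replacing chi-square with Fisher everywhere would also cost sensitivity to real harm. For true rates of 15% v 2%, power falls from 61% to 33%; for 10% v 1%, from 41% to 13%. It would change the test for well-filled variables such as sex, where chi-square is adequate.

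A reader might infer three stronger things that the documents do not support:

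- That the protocol's figures show adverse events will be sparse. No rate is given. The manufacturer's statement concerns benzyl alcohol, whereas the two-week contact (Study Design) asks about any adverse effect after the procedure, in both arms. At the 25% suspension threshold, the expected count at 76 patients would be 76 × 0.25/2 = 9.5.
- That the accrual table demonstrates a safety problem. Those are race and ethnicity targets. With 2 Hispanic patients, chi-square cannot reach 0.05 at all, and for the 2/6/68 race table the chance of p < 0.05 under random allocation is about 2.5%. Baseline comparisons decide nothing in this plan.
- That this is the only safety comparison between arms. Adverse Event Stopping Rule and Protection also compare adverse events between arms, without naming a test.

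**Conclusion.** The gap holds, and it is minor. Chi-square is the only test named for counts, and no provision is made for sparse tables. If 9 or fewer of 76 patients have an adverse event, the stated rule can label a chance split significant when all three exact tests examined do not (4 v 0 and 6 v 1 at 38 per arm). It should not be read as a general inflation of false positives: the overall rate peaks near 5.8% and is 4.1% or less at event rates of 5% or below.

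The conclusion assumes equal arms of 38, uncorrected Pearson chi-square and independent patients. That the final adverse event table will be sparse is a plausible inference from the low-risk wording, not a stated figure. The primary pain comparison, the sample size of 76 and the adverse event suspension rule do not depend on this test.

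**What to change.** In Data Analysis, keep chi-square for well-filled tables and add a sentence to this effect: where any expected count is below 5, an exact test will be used, namely an unconditional test (Barnard or Boschloo) for 2×2 tables and the Fisher-Freeman-Halton test for larger ones. Fisher is acceptable for 2×2 tables if an unconditional test is not available in the planned software. Commit to one test before the data are seen, because the exact tests themselves disagree at 5 v 0 and 7 v 1.

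Add that the between-arm difference in the percentage of patients with an adverse event will be reported with an exact 95% confidence interval, whatever the p-value.

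The cost is two sentences of analysis text and an exact option in the software; no design change is needed. The downside is that exact tests, Fisher most of all, are less sensitive to a real difference in harm, which is why the interval should always be reported. The cut-off at 5 is a convention and will not remove every disagreement; 8 v 2 would still be judged by chi-square.

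### Two aims are called primary with no testing order, the hip-injection rating is missing from the Data Analysis comparison, and a difference test cannot support Hypothesis 2

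*Combined protocol and SAP*

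**What the plan says.** All places are in the combined protocol and SAP.

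- **Primary Aims** lists two items under one heading. The first is "To compare subcutaneous/intramuscular infiltration pain of BS versus buffered 1% lidocaine" before the procedure; the second is "To compare local anesthesia efficacy of BS versus buffered 1% lidocaine" during it.
- **Hypotheses** gives each aim its own statement. The second is "US guided intraarticular hip injections are equally or less painful after local anesthesia with BS versus buffered 1% lidocaine infiltration".
- **Study Design** defines three VAS ratings: baseline hip pain, infiltration pain, and hip joint injection pain.
- **Sample Size** names one outcome: "The primary outcome will be the VAS for Pain score during local anesthesia infiltration". It continues: "We will use two-sample t-tests to compare the mean VAS for Pain scores between the two groups at each of the three time points".
- **Data Analysis** has a narrower list: "The mean VAS for Pain score prior to and during local anesthesia infiltration will be compared between the 2 groups", by t-test or Wilcoxon test. It adds change-from-baseline tests, a GLM adjusted for age, gender and baseline VAS, and mixed models. None of these names the hip-injection rating or a contrast for it.
- **Data Analysis** closes with one rule for everything: "For all analyses, two-sided tests will be used and p-values less than 0.05 will be considered as statistically significant". No hierarchy, adjustment or non-inferiority margin appears anywhere.

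**The concern.** Three things do not fit together.

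1. Two aims carry the primary label, but only one has the primary outcome, and every p-value below 0.05 has the same standing. A trial that missed on infiltration pain could still present the hip-injection result as a positive primary finding, and nothing in the plan would contradict it.
2. The section an analyst would work from drops the rating that shows whether BS works as an anesthetic. It keeps a between-group test of baseline pain, which is measured before any anesthetic is given.
3. Hypothesis 2 says that BS is no worse. The planned test asks whether the arms differ. If it is not significant, the likely report is similar efficacy, which that test cannot establish. The Strengths section rests the case for changing practice partly on similar efficacy.

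**Working it through.** **Inputs.** From Sample Size: difference 14 mm, SD 20 mm, α = 0.05, power 80%, 34 per group, 10% dropout, total 76. Data Analysis says that tests are two-sided. The documents give no correlation between ratings and no margin; values for these below are assumptions, shown as ranges.

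**1. The plan's own figure.** Normal approximation: n = 2σ²(z₀.₉₇₅ + z₀.₈₀)²/Δ² = 2 × 400 × (1.960 + 0.842)²/196 ≈ 32.0, rounded up to 33. The exact noncentral t gives 33.02, rounded up to 34. Power is 81.2% at 34 per group and 79.97% at 33. Dropout: 68/0.9 = 75.6, so 76. The stated sample size reproduces, for one outcome tested at 0.05.

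**2. Error rate.** For infiltration VAS alone it is 5%. If either aim may be claimed at two-sided 0.05, the rate with no true difference is 1 − P(|Z₁| ≤ 1.96 and |Z₂| ≤ 1.96), with Z₁ and Z₂ bivariate normal with correlation ρ. At ρ = 0 this is 1 − 0.95² = 9.75%. For a false finding in favor of BS, each test contributes 2.5%, so at ρ = 0 it is 1 − 0.975² = 4.94%.

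| Assumed ρ | Either aim, any direction | Either aim, favoring BS |
|---|---|---|
| 0 | 9.75% | 4.94% |
| 0.3 | 9.51% | 4.76% |
| 0.5 | 9.07% | 4.54% |
| 0.7 | 8.35% | 4.17% |
| 0.9 | 7.04% | 3.52% |

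**3. Cost of controlling it.** A Bonferroni split (0.025 per aim) needs 41 per group by exact t (40.08 rounded up). That is 82 evaluable and 82/0.9 = 91.1, so 92 in total; at 34 per group the power would be 72.2%. A fixed sequence keeps 0.05 for the first test, 81.2% power and N = 76.

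**4. What the Aim 2 data can show.** With 34 per group and SD 20, the 95% CI half-width is t₀.₉₇₅,₆₆ × 20 × √(2/34) = 1.9966 × 4.851 ≈ 9.7 mm. Suppose the observed BS minus lidocaine difference were 9 mm, against BS. The interval would run from 9 − 9.7 = −0.7 to 9 + 9.7 = 18.7 mm. The difference test is not significant, yet the interval includes differences above the protocol's 14 mm.

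**5. Candidate margins** (true difference 0, SD 20, one-sided 0.025, 80% power, normal approximation: n = 2σ²(1.960 + 0.842)²/M²):

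| Assumed margin M | n per group | Observed difference must be below (M − 9.7) |
|---|---|---|
| 14 mm | 33 | 4.3 mm |
| 10 mm | 63 | 0.3 mm |
| 7 mm | 129 | −2.7 mm |

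The planned size supports a margin of 14 mm. It is too small for 80% power at 10 or 7 mm.

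**The case against.** The strongest reply is that Sample Size names a single primary outcome and sizes the trial on it alone, so the primary error rate is 5%, and the rest is a mismatch of wording between two sections. Much of this stands, and it rules out three stronger readings.

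- *A reader might infer that the efficacy aim has no test.* It has one. Sample Size plans a t-test "compare the mean VAS for Pain scores between the two groups at each of the three time points", and Study Design makes hip-injection pain the third. The fault is that Data Analysis leaves it out, so the two sections disagree.
- *A reader might infer that the trial's false-positive rate is close to 10%.* The documents nowhere say that success on either aim makes the trial positive. The 9.75% also needs uncorrelated ratings, although both come from the same patient in one visit. If they are positively correlated, the rate is lower.
- *A reader might count all three time points toward the error rate.* Baseline pain is rated before treatment, so a chance imbalance there cannot be reported as a treatment effect. The GLM already uses it as a covariate.

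It is also fair to say that with no true difference Hypothesis 2 is true. The table above therefore concerns false claims of a difference, not false claims that BS is no worse.

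The reply does not remove the primary label on Aim 2 or supply an order. Nor does it make a difference test able to show that BS is no worse.

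**Conclusion.** The point holds in limited form, and the plan should be changed. The error rate is 5% for the named primary outcome. It is about 7.0% to 9.75% only if either aim may be claimed alone, for assumed correlations from 0.9 to 0; in favor of BS it is 3.5% to 4.9%, against 2.5%. The plan does not say that either aim may be claimed, but it does not prevent it.

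The more consequential part is Aim 2. Data Analysis omits its rating, and the test given in Sample Size answers a different question from Hypothesis 2. This conclusion does not depend on the assumed correlation. The CI half-width of 9.7 mm rests on the SD of 20 from Sample Size applying to hip-injection pain as well, and on 34 evaluable patients per group.

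**What to change.** In Data Analysis:

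- **(a)** Name infiltration VAS and hip-injection VAS as the two between-group comparisons, in line with Sample Size. Use baseline VAS as a covariate and drop it as an outcome test.
- **(b)** Test infiltration VAS first at two-sided 0.05. Treat Aim 2 as confirmatory only if that result is significant in favor of BS.
- **(c)** Base the Aim 2 conclusion on the BS minus lidocaine difference in hip-injection VAS with its 95% CI. Conclude that BS is no more painful only if the upper limit lies below a margin stated in advance. The only candidate figure in the protocol is 14 mm, and it is given there as a minimal clinically important difference, not as a margin. The sponsor should justify it for this use or choose a smaller one, knowing that 10 or 7 mm would need about 63 or 129 per group for 80% power.
- **(d)** Label all other tests exploratory.

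With a justified 14 mm margin this is a wording change: N stays at 76 and power for the primary outcome at 81%. The downside is that Aim 2 cannot be claimed as confirmatory if Aim 1 fails. That agrees with Sample Size, which already puts infiltration VAS first.
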